## Measurements and Measurement Instruments

### 1 repetition maximum:

The same investigators will administer all strength testing. In short, after a brief general warm-up, a specific warm-up of the given exercise will be performed at approximately 50% of the participant's estimated 1RM based on the 10RM testing. Load will be progressively increased by approximately 10-20% for each repetition until a true 1RM will be reached as previously described (39). Three to 5 min of rest was given between each attempt. A successful attempt required the participant to move the load throughout the full range of motion with correct form.

### VO2peak

Subjects will complete double-leg and single-leg incremental peak oxygen uptake (VO2peak) tests on a cycle ergometer (Velotron, RacerMate; Seattle, WA). A metabolic cart with an on-line gas collection system (Moxus modular oxygen uptake system, AEI Technologies, Pittsburgh, PA) will acquire oxygen consumption (VO2) and carbon dioxide production (VCO2) data and heart rate will be monitored continuously with a heart rate monitor (Polar A3, Lake Success, NY). The test will begin with a 1-min warm up at 50 watts (W), after which the power will be increased by 1 W every two seconds until volitional exhaustion or the point at which pedal cadence falls below 60 rpm. Heart rate will be monitored continuously throughout the test via telemetry with a heart rate monitor (Polar, Kempele, Finland). A similar protocol will be used for single-leg tests, except that power will increase by 1 W every *four* seconds. VO2peak and will be defined as the highest oxygen consumption achieved over a 30-s period. Maximal workload (Wmax) will be the highest power output achieved during the test. The subject is deemed to have reached VO2peak if: i) the perceived exertion is >19 (Borg Scale) ii) his HR is within 5bpm of age-predicted maximal HR; iii) his RER is >1.2; and iv) a plateau has been reached in their oxygen consumption.

### DXA Scan:

Body composition (i.e. fat (%), appendicular lean mass (kg), and lean body mass (kg)) will be determined by dual-energy x-ray absorptiometry (DXA).

### Deuterated Water:

Deuterium is an isotope of hydrogen and is in fact already present in small amounts in the water consumed daily (i.e. 0.02%). It poses no health risk in the quantities consumed during this study, and about half of the water in the body is replaced every week. Once the participant stops drinking this water, body water will return to its normal concentration in 20-30 days. During the study, participants will be required to drink ~1 cup of deuterated water (D2O).

### Skeletal Muscle Biopsies and Analyses:

During the study, 7 muscle biopsies will be collected (days -3, 0 [4 biopsies], 1, and 2). This procedure involves the removal of a small piece of muscle tissue using a sterile hollow needle from the quadriceps muscle (*vastus lateralis*) under local aesthetic (lidocaine). A small piece of muscle (~100 mg) will be

collected at each time point. Following the biopsies, the incisions will be closed with instant medical adhesive, and wrapped with a tensor bandage. Phosphoproteomic analysis will be conducted by mass-spectrometry as previously described (41). Myofibrillar MPS will be calculated using the precursor-product equation: myofibrillar MPS =  $([E_{2b}-E_{1b}]/[E_{ic} \times t]) \times 100$ .  $E_b$  represents the enrichment of bound myofibrillar protein,  $E_{ic}$  is the average intracellular enrichment between two biopsies, and  $t$  is the tracer incorporation time in h. As we will employ 'tracer naïve' participants (had not previously participated in a study protocol where L-[*ring*-C6] phenylalanine was infused), a pre-infusion blood sample will be used for the calculation of resting myofibrillar MPS (50). Myofibrillar and intracellular enrichments of L-[*ring*-C6] phenylalanine will be measured as previously described (51). Integrated (i.e., days) rates of muscle protein synthesis (MPS) will be determined using the D2O method. Briefly, H enrichment of saliva (precursor) and muscle (product) pools (relative to H) will be determined using isotope ratio mass spectrometry and myofibrillar fractional synthetic rate determined, as previously described (52, 53).

Diets:

*Ad libitum* 3-day dietary records for each participant will be collected and analyzed for baseline macronutrient intake. During the study, all food will be provided to the participants as frozen meals (Supplier: Copper County Foods), and pre-weighed and measured snack items.

Physical activity:

Recreationally active young men (assessed through physical activity questionnaire) will be recruited. Participants will be asked to maintain their habitual activity for the duration of the study.

Exercise Protocol:

Resistance exercise: 5 sets × 10 reps 75% 1RM leg press followed by leg extension, with 2 min recovery between sets and exercises (50).

Endurance exercise: 4 × 5 min @ 65% single leg peak power with 2.5 min recovery @ 20% peak power (MacInnis 2016)

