### **Posttranslational modification of proteins**

Key to exercise-induced adaptation is post-translational modification of proteins. One important post-translational modification is known as phosphorylation. Phosphorylation is the addition of a phosphate group to a target protein by a protein kinase using ATP and Mg (39). The addition of this phosphate can promote the catalytic activity or binding status of a protein resulting in a biological downstream effect. There are over 500 kinases in the human 'kinome'. We (39, 40) and others (16) often assess the phosphorylation status of single or multiple (~ten) kinases/proteins in response to exercise to gain a mechanistic understanding of how exercise alters the skeletal muscle phenotype. However, current methods are largely semi-quantitative (Western blotting) and are biased in terms of which proteins are studied (i.e., the experimenter can only select a limited number of kinases/proteins to measure). Our understanding of how skeletal muscle adaptation is influenced by phosphorylation is therefore limited. Recent developments in mass spectrometry (41, 42) have enabled a wider interrogation of the phosphorylation status of proteins in response to exercise. Indeed, one study, using advanced liquid chromatography-mass spectrometry, revealed 1,004 unique exercise-regulated phosphorylation sites on 562 proteins in human skeletal muscle biopsy samples obtained before and after a bout of endurance exercise (41). This seminal finding has significantly advanced our knowledge regarding how endurance exercise impacts phosphorylation. Yet, no measurements of end-point MPS were made. Moreover, comparable work has not been performed with resistance exercise. The aim of our investigation is to conduct a similar global phosphoproteomic analysis of skeletal muscle using advanced mass spectrometry following both endurance and resistance exercise in humans. We will also directly measure rates of MPS for the 3 hours following exercise.

The aim of our investigation is to conduct a similar global phosphoproteomic analysis of skeletal muscle using advanced mass spectrometry following resistance and aerobic exercise in humans.

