## **Methodology**

A schematic illustration of the experimental design and experimental trial can be seen in Figures 1 and 2, respectively. In a within-subject repeated measures cross-over design, 12 participants (6 male and 6 female) will attend the laboratories at the Dept. of Kinesiology on 6 separate occasions. On the first occasions participants will be assessed for body composition using dual-energy x-ray absorptiometry (DXA) after an overnight fast (~10 hours) followed by familiarization on resistance exercise and endurance exercise equipment. At this point, your two legs will be randomly assigned to the resistance exercise or endurance exercise group.

On the second visit, participants will perform a 1-repetition maximum test on a leg press and leg extension machine. These tests will be used to determine the workload performed on the experimental trials. On the third visit participants will perform a  $V_{02\text{ max}}$  test on a cycle ergometer to determine their aerobic fitness. On the same day, subjects will be familiarized with single-leg cycling. On visit 4, subjects will perform another  $V_{02\text{ max}}$  test on a cycle ergometer using one leg only. This test will determine the intensity of cycling performed on the experimental trial. To ensure the intensity is appropriate, the subjects will be familiarized with the experimental trial training programs (see “Exercise protocols” below).

Subjects will then embark on a 3-day period of controlled diet and exercise followed by experimental trials (visits 5 and 6) separated by 1 week. The reason for the two independent trials is that the measurement of MPS requires the

infusion of a stable amino acid isotope (L-[*ring*-C6] phenylalanine), which interferes with the assessment of the phosphoproteome due to the fact they both detect changes in protein mass. Thus the first trial will be conducted to assess exercise-induced changes in the phosphoproteome and the second for MPS, using the L-[*ring*-C6] phenylalanine isotope.

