#### Acute protocols (Visits 5 + 6)

On visit 5 participants will arrive at the laboratory at approximately 0640 after a 10h overnight fast. After a brief assessment, subjects will rest on a bed for 3 hours. After this period, a skeletal muscle biopsy will be obtained and participants will perform a bout of resistance exercise with a randomised leg, followed by a bout of endurance exercise. Skeletal muscle biopsies will again be obtained immediately following both bouts of exercise and again 3h following exercise. On visit 6, participants will again arrive at the laboratory at approximately 0640 after an overnight fast. This time, a catheter will be placed in the upper forearm. After the placement of the catheter, a primed constant infusion of L-[*ring*-C6] phenylalanine will be commenced to measure rates of MPS and a catheter placed in the contralateral arm for repeated blood sampling. Exercise and skeletal muscle biopsies will be obtained as in visit 5 (see Figure 2). We have routinely obtained ethical approval and published papers for studies that employ skeletal muscle biopsies and stable amino acid tracers in human volunteers (3, 14, 44-49). [name], a licenced physician, has approved our standard operating procedure and will oversee all muscle biopsy and catheter infusions.

[figure not shown]
[figure not shown]

Figure 1 Schematic illustration of experimental design.

**R.Ex-** 3 sets  $\times$  10 reps 70% 1RM leg press followed by leg ext.  
2 min recovery between sets and exercises.

**E.Ex-** 4  $\times$  5 min @ 65% single leg peak power  
w/ 2.5 min recovery @ 20% peak power.

\* Timing will change depending on exercise order

Figure 2. Schematic illustration of Visit 6.

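### The list of seven biopsies on days -3 to 2 cannot hold the two identical biopsy visits planned one week apart

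*Combined protocol and SAP*

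**What the plan says.** Skeletal Muscle Biopsies and Analyses gives a count for the whole study and the days on which tissue is taken: "7 muscle biopsies will be collected (days -3, 0 [4 biopsies], 1, and 2").

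The Methodology section describes a different calendar. Participants "will attend the laboratories at the Dept. of Kinesiology on 6 separate occasions", and the last two are the "experimental trials (visits 5 and 6) separated by 1 week". They are preceded by a lead-in: "Subjects will then embark on a 3-day period of controlled diet and exercise". Two trials are needed because the infused tracer interferes with the phosphoproteome assay: "Thus the first trial will be conducted to assess exercise-induced changes in the phosphoproteome and the second for MPS".

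Acute protocols (Visits 5 + 6) sets out the tissue sampling. Visit 5 has a resting biopsy before exercise, and then "Skeletal muscle biopsies will again be obtained immediately following both bouts of exercise and again 3h following exercise". For visit 6, "Exercise and skeletal muscle biopsies will be obtained as in visit 5". No biopsy is described at visits 1 to 4.

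The background section on posttranslational modification adds: "We will also directly measure rates of MPS for the 3 hours following exercise".

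**The concern.** Both passages tell staff when to take muscle, and they cannot both be followed. One gives a single day with several biopsies and single biopsies on three other days. The other gives two full biopsy sets a week apart.

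If staff work from the seven-biopsy list, one experimental visit yields no tissue and its outcome is lost. Which outcome that is depends on which visit is day 0, and the text does not say. If day 0 is visit 5, infusion MPS at visit 6 has no muscle sample, although the precursor-product equation needs the enrichment of bound muscle protein. If day 0 is visit 6, the primary phosphoproteome outcome has no sample.

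If staff work from the Acute protocols section, the stated figure of 7 is not the number of biopsies a participant undergoes. In a study of healthy volunteers, the number of invasive procedures should be a figure that can be relied on.

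**Working it through.** **Inputs.** From Skeletal Muscle Biopsies and Analyses: 1 biopsy on day -3, 4 on day 0, 1 on day 1, 1 on day 2. From Methodology: visits 5 and 6 are 7 days apart, and there are 6 attendances. From Acute protocols: biopsies at rest, immediately after exercise and at 3 h, repeated identically at visit 6. The number per leg at each time is not given.

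**Step 1: the stated total.** 1 + 4 + 1 + 1 = 7. The list is arithmetically correct on its own terms.

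**Step 2: calendar.** The widest gap between listed days is 2 - (-3) = 5 days. The visits are 7 days apart, so no pair of listed days can be visits 5 and 6. Whichever visit is day 0, the other falls on day 7 or day -7, and neither is listed.

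**Step 3: capacity.** Each visit has three sampling times, so it needs at least 3 biopsies. Only day 0 has more than 1. At most one visit fits, and at 5 or 6 biopsies per visit even day 0, with 4, is too small.

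**Step 4: what the two visits need.** Per visit, n = rest + immediately after + 3 h, with 1 or 2 biopsies at each time, so n runs from 3 to 6. The two visits need 2n. Adding the single biopsies on days -3, 1 and 2 gives 2n + 3.

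| Biopsies per visit (n) | Two visits alone (2n) | With days -3, 1 and 2 (2n + 3) |
|---|---|---|
| 3 | 6 | 9 |
| 4 | 8 | 11 |
| 5 | 10 | 13 |
| 6 | 12 | 15 |

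One biopsy at rest and one per leg at each post-exercise time gives n = 1 + 2 + 2 = 5. Two identical visits always give an even total, so they cannot by themselves make 7.

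**Step 5: attendances.** The two visits are already within the stated 6. Days -3, 1 and 2 match no biopsy visit in Methodology. Keeping them gives 6 + 3 = 9 attendances, or 6 + 2 = 8 if day -3 falls on the date of visit 4.

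**Step 6: readings that might remove the conflict.**
- Days numbered afresh around each visit give 7 × 2 = 14 biopsies, but the count of 7 is stated for the whole study.
- A single day serving both outcomes is ruled out by the stated reason for having two trials.

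**The case against.** The strongest reply is that two designs have been left side by side and should not be added together. The seven-biopsy list reads like a single trial with deuterated-water (D2O) MPS measured over days, while Methodology and Acute protocols read like a two-trial infusion design. On that view a combined total describes a schedule that nobody planned. This stands as a limit on the numbers: the right-hand column of the table applies only if the sponsor wants both. It does not remove the conflict, because both passages are current text.

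A reader might infer three stronger things, none of which the documents support:
- **That 7 is too low by a known amount, for example 4 against a total of 11.** That figure assumes that both schedules are kept and that each visit has 4 biopsies. Acute protocols gives no count per visit, and at 3 per visit the two visits alone need 6, which is below 7.
- **That following Acute protocols breaks the stated 6 attendances.** It does not. The extra attendances come only from days -3, 1 and 2.
- **That infusion MPS is the outcome that would be lost.** The 3-day lead-in makes visit 5 the more natural day 0, but the text does not say so. With day 0 at visit 6, the outcome without tissue is the primary one.

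Figures 1 and 2 are not shown in the text reviewed and may settle the number of biopsies per visit. They cannot fit a 7-day gap into a list that spans 5 days.

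**Conclusion.** The inconsistency is real and must be fixed. The biopsy list can hold at most one of the two experimental visits, whatever the count per visit. That conclusion needs no assumption beyond the two passages and the one-week interval.

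The size of the correction is conditional. The two visits alone need 6 to 12 biopsies (10 with one at rest and one per leg at each later time) and the stated 6 attendances. If days -3, 1 and 2 are kept as well, the total is 9 to 15 (11 at 4 per visit, 13 at 5), with 8 or 9 attendances. These ranges assume 1 or 2 biopsies at each sampling time. The correct total within them is for the sponsor to state.

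**What to change.** Replace the count and day list in Skeletal Muscle Biopsies and Analyses with one schedule that follows Acute protocols at both visits. It should:
- say which visit is day 0 (visit 5 fits the lead-in, which puts visit 6 on day 7);
- give the number of biopsies per leg and time point;
- mark whether each biopsy serves the phosphoproteome, infusion MPS or D2O MPS;
- carry one total of biopsies and one total of attendances, used throughout.

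If burden must be limited, first consider dropping the single biopsies on days -3, 1 and 2, which appear to serve only the D2O measure. No objective or hypothesis names integrated D2O MPS, and it is described only for myofibrillar protein, so it does not cover the mitochondrial hypothesis. A cap of 7 would then be met only at 3 biopsies per visit (6 in all).

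Dropping infusion MPS instead would cost more. It would also mean amending the background statement on MPS over 3 h, Specific Objectives, Hypotheses, Methodology and Acute protocols.

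The cost of the main fix is one schedule table and amended text. The stated burden may rise, because the true figure may be above 7.

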## Specific Objectives

1. Our primary objective is to examine the effect of resistance exercise on the human skeletal muscle phosphoproteome.
2. Our secondary objective is to assess changes in rates of myofibrillar and mitochondrial MPS following resistance and endurance exercise.

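### The resistance bout is prescribed two ways, 3 × 10 at 70% 1RM and 5 × 10 at 75% 1RM, and the protocol does not say which governs

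*Combined protocol and SAP*

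**What the plan says.** The resistance bout is described in two places.

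- **Exercise Protocol** (at the end of the section headed Skeletal Muscle Biopsies and Analyses): "Resistance exercise: 5 sets × 10 reps 75% 1RM leg press followed by leg extension", with 2 min of recovery.
- **Acute protocols (Visits 5 + 6)**, in the text between the captions of Figures 1 and 2: 3 sets of "10 reps 70% 1RM leg press followed by leg ext", with "2 min recovery between sets and exercises".

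Two other sentences bear on which text applies. The visit 4 description in Methodology says "the subjects will be familiarized with the experimental trial training programs (see “Exercise protocols” below". The visit 6 description says "Exercise and skeletal muscle biopsies will be obtained as in visit 5 (see Figure 2".

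Methodology also explains the purpose of the two trials: "Thus the first trial will be conducted to assess exercise-induced changes in the phosphoproteome and the second for MPS". Under Specific Objectives the protocol states: "Our primary objective is to examine the effect of resistance exercise on the human skeletal muscle phosphoproteome".

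**The concern.** The primary objective concerns the effect of resistance exercise, and hypotheses 2 and 3 compare resistance with endurance exercise on myofibrillar and mitochondrial protein synthesis. If the resistance bout has two definitions, the exposure in the primary objective and one side of both comparisons are not uniquely specified. A reader of the results could not tell from the protocol which bout was planned.

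There is also a risk in delivery. Staff working from one place rather than the other could give different bouts to different participants, or to the same participant at visits 5 and 6. With 12 participants planned and some attrition expected, such a mixture would be hard to separate from between-person or between-visit variation. It would also weaken any link drawn between the phosphoproteome at visit 5 and protein synthesis at visit 6, which presupposes the same stimulus at both.

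**Working it through.** **Inputs, side by side**

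| Element | Text with the schematics, Acute protocols | Exercise Protocol |
|---|---|---|
| Exercises, in order | leg press, leg extension | leg press, leg extension |
| Sets | 3 | 5 |
| Repetitions per set | 10 | 10 |
| Load, % of 1RM | 70 | 75 |
| Recovery | 2 min | 2 min |
| Endurance bout | 4 × 5 min at 65%, 2.5 min at 20% | 4 × 5 min at 65%, 2.5 min at 20% |

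The resistance bout differs in sets and in load. The endurance bout is identical in both places.

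**Size of the difference**

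The protocol gives no figure for total work, so there is none to reproduce. As a simple summary, take volume-load per exercise = sets × repetitions × %1RM. Workload comes from one 1RM test visit (visit 2), so a participant's 1RM is common to both versions and cancels in the ratio.

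- Text with the schematics: 3 × 10 × 70 = 2,100
- Exercise Protocol: 5 × 10 × 75 = 3,750
- Ratio: 3,750 / 2,100 = 1.79
- Components: sets 5/3 = 1.67; load 75/70 = 1.07; product 1.79

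If the stated sets apply to each exercise, which both places imply but neither spells out:

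- Total sets: 3 × 2 = 6 versus 5 × 2 = 10
- Total repetitions: 6 × 10 = 60 versus 10 × 10 = 100
- Scheduled rest within the bout: (6 − 1) × 2 = 10 min versus (10 − 1) × 2 = 18 min

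**Could both texts be right, for different purposes?**

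1. *Different visits.* The visit 6 description says exercise is obtained as in visit 5. That is most naturally read as one bout used at both.
2. *Familiarisation versus trial.* The visit 4 sentence sends the reader to the exercise section for the programs of the experimental trial itself, so that section is not a separate familiarisation bout.
3. *Shorthand beside the figure.* The text there states sets, repetitions, load and recovery in full, and its endurance line matches the Exercise Protocol exactly. It reads as a complete prescription.
4. *A precedence rule.* There is none. The visit 4 sentence points to the exercise section and the visit 6 sentence points to Figure 2. Neither says that one overrides the other.
5. *Superseded or damaged text.* Neither version comes from a change log or a redaction. A reading error in the PDF would have to have altered two separate numbers.

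**The case against.** The contradiction itself is not in dispute. The case on the other side concerns certainty and weight.

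- *Attribution to Figure 2 is inferred.* The figures are not visible, and the 3 × 10 text sits between two captions. This stands as a caveat. The asterisked note there on timing and exercise order fits the visit 6 schematic, but the conflict is the same whichever figure the text belongs to.
- *The two pointers are not equivalent.* The one in Methodology names the training programs. The one to Figure 2 closes a sentence about exercise and biopsies, and may refer only to sequence and timing. This is fair, but the Methodology pointer is attached to visit 4 familiarisation and sets no precedence.
- *The reach to visit 5 rests on one loosely worded sentence.* This is also fair: the Figure 2 caption names visit 6 only. A single bout for both visits is the natural reading rather than a proven one. If the bouts were meant to differ between visits, the protocol would need to say so, and it does not.
- *Mixed delivery is speculative.* The study is small, runs in one laboratory, calls itself an observational pilot and familiarises participants beforehand. Nothing shows that staff would work from different pages. If one version is used throughout, the harm is confined to the document. This stands, and the finding does not depend on mixed delivery having occurred.
- *Volume-load is not a quantity the protocol uses.* Correct. It conveys scale only; the plain differences in sets and load are enough to establish the conflict.

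**Conclusion.** The concern holds. The protocol gives two incompatible prescriptions for the resistance bout: 3 versus 5 sets of 10, and 70% versus 75% of 1RM, with the same exercises and recovery. In volume-load the gap is 1.79-fold, assuming all sets are completed at the prescribed load with a common 1RM. The totals of 6 versus 10 sets and 60 versus 100 repetitions further assume that the set count applies to each exercise.

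It must be corrected because the intervention in the primary objective, and in one side of hypotheses 2 and 3, is not uniquely defined. That ground is sufficient without any claim about inconsistent delivery. The reach to the primary outcome at visit 5 relies on reading visit 6 exercise as the same bout as visit 5. No claim is made that phosphorylation or protein synthesis changes in proportion to volume-load.

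**What to change.** Reconcile the text accompanying the schematics in Acute protocols (Visits 5 + 6) with the Exercise Protocol, so that the document carries one prescription of sets, repetitions and percentage of 1RM. State it once, make explicit whether the set count applies to each exercise, and cross-reference it from the visit 4 familiarisation in Methodology and from the descriptions of visits 5 and 6. Which prescription is right is for the investigators to settle; this review takes no position.

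The cost is a short correction to one of the two places plus the cross-references. Visits, sample size and assays do not change.
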